3.2 Exclusion Criteria

1. Prior malignancy active within the previous 2 years except for locally curable cancers that have been apparently cured, such as basal or squamous cell skin cancer, superficial bladder cancer, carcinoma in situ of the cervix or breast, or localized prostate cancer. If patients have another malignancy that was treated within the last 2 years, such patients may be enrolled if the likelihood of requiring systemic therapy for this other malignancy within 2 years is less than 10%, as determined by an expert in that particular malignancy at MD Anderson Cancer Center and after consultation with the Principal Investigator.
2. Any major surgery, radiotherapy, chemotherapy, biologic therapy, immunotherapy, experimental therapy within 4 weeks prior to the first dose of the study drugs. For oral targeted therapies (such as ibrutinib, idelalisib, venetoclax), a washout of 3 days is allowed. Note: Prior treatment with anti CD20 monoclonal antibody, anti CD52 monoclonal antibody and lenalidomide are allowed. Prior treatment with anti-CTLA-4 and anti-PD1 therapies is allowed after a wash-out of 5 half-lives.
3. Significant cardiovascular disease such as uncontrolled or symptomatic arrhythmias,

congestive heart failure, or myocardial infarction within 2 months of screening, or any Class 3 or 4 cardiac disease as defined by the New York Heart Association Functional Classification.

4. History of stroke or cerebral hemorrhage within 2 months.
5. Patients who have uncontrolled hypertension (defined as sustained systolic blood pressure \geq 160 mmHg or diastolic \geq 100 mmHg).
6. Known evidence of active cerebral/meningeal CLL. Patients may have history of CNS leukemic involvement if definitively treated with prior therapy and no evidence of active disease at the time of registration.
7. Active, uncontrolled autoimmune hemolytic anemia or immune thrombocytopenia requiring steroid therapy.
8. Patients with autoimmune diseases are excluded: Patients with a history of Inflammatory Bowel Disease (including Crohn's disease and ulcerative colitis) are excluded from this study as are patients with a history of autoimmune disease (e.g., rheumatoid arthritis, systemic progressive sclerosis, systemic lupus erythematosus, Wegener's granulomatosis).
9. Patients with previous allogeneic stem cell transplant (SCT) within 6 months or with active acute or chronic graft-versus host disease are excluded. Patients must be off immunosuppression for GVHD for at least 60 days before cycle 1 day 1.
10. Patients with organ allografts (such as renal transplant) are excluded.
11. History of any hepatitis (e.g., alcohol or non-alcohol steatohepatitis (NASH), auto immune, or grade 3-4 drug-related hepatitis).
12. Patients who are on high-dose steroids (doses $>$ 10mg/day of prednisone or equivalent) or immune suppression medications. Note: Patients on high-dose steroids (doses $>$ 10mg/day of prednisone or equivalent) or immune suppression medications are eligible provided these drugs are discontinued at least 3 days prior to starting on the study drugs.
13. Patients with uncontrolled active infection (viral, bacterial, and fungal) are not eligible.
14. Current or chronic hepatitis B or C infection, or known seropositivity for HIV.
15. Patient is pregnant or breast-feeding.
16. Concurrent use of investigational therapeutic agent
17. Patients may not receive other concurrent chemotherapy, radiotherapy, or immunotherapy. Localized radiotherapy to an area not compromising bone marrow function does not apply.
18. Other severe acute or chronic medical or psychiatric condition or laboratory abnormality that in the opinion of the investigator may increase the risk associated with study participation or investigational product administration or may interfere with the interpretation of study results and/or would make the patient inappropriate for enrollment into this study.

4.0 TREATMENT PLAN

4.1 Study Design

This is a phase II open label single-arm study to evaluate combined lirilumab and rituximab in patients with CLL.

	C1D1	C1D8 (±2 days)	C1D15 (±2 days)	C1D22 (±2 days)	C2-C12 D1 (±7 days)	C13-C24 D1 (±7 days)
Rituximab	375 mg/m ²	375 mg/m ²	375 mg/m ²	375 mg/m ²	375 mg/m ²	–
Lirilumab	3 mg/kg	–	–	–	3 mg/kg	3 mg/kg

Each cycle is 4 weeks. Patients will receive rituximab (375 mg/m² IV) weekly for the first 4 weeks (Days 1, 8, 15, 22), and then with the start of each course. Lirilumab (3 mg/kg IV) will be given on day 1 of each cycle. Rituximab will be given for the first 12 cycles and lirilumab will continue for up to 24 cycles.

5.0 STUDY MEDICATIONS

5.1 Lirilumab

5.1.1 Preparation and Dispensing of Lirilumab

The product storage manager should ensure that the study drug is stored in accordance with the environmental conditions (temperature, light, and humidity) as determined by the Investigator Brochure. If concerns regarding the quality or appearance of the study drug arise, do not dispense the study drug and contact the sponsor immediately.

Investigational product documentation must be maintained that includes all processes required to ensure drug is accurately administered. This includes documentation of drug storage, administration and, as applicable, storage temperatures, reconstitution, and use of required processes (e.g. required diluents, administration sets).

Care must be taken to assure sterility of the prepared solution as the product does not contain any anti-microbial preservative or bacteriostatic agent. The study drug should be administered shortly after preparation in order to avoid exposure of the prepared drug to room temperature conditions beyond a recommended 4 hour limit. This 4 hour time limit at room temperature includes the time allotted for IV dose administration, which is 60 min. In the event that a delay in use of prepared (diluted) study drug is anticipated, prepared bags may be refrigerated for a maximum of 20 hours. Study drug is to be administered as IV

2014-0933 Lirilumab and Rituximab for Relapsed/Refractory CLL

Version 2 – November 05, 2015

Page 10 of 27

infusion and not IV push or bolus injection.

Lirilumab must be stored at a temperature of 2°C to 8°C and should be protected from light and from freezing. For details on prepared drug storage and use time of lirilumab under room temperature/ light and refrigeration, please refer to the Investigator Brochure.

Unused or expired lirilumab vials will be disposed per MDACC guidelines.

5.1.2 Administration of Lirilumab

Please refer to the Investigator Brochure

5.2 Rituximab

Rituximab is anti-CD20 monoclonal antibody. Commercial drug supply will be used for this study. Rituximab will be administered as per the institutional guidelines.

6.0 DOSE DELAYS AND MODIFICATIONS

Patients who experience Grade 3 or 4 toxicity that can be clearly attributed to either lirilumab or to rituximab may continue treatment with the other agent while the causative agent is delayed until resolution of toxicity to grade ≤ 1 or baseline. In cases where Grade 3 or 4 toxicity cannot be attributed to a specific study drug, both study drugs should be held regardless of attribution of toxicity until the toxicity is resolved to grade ≤ 1 or baseline.

Rituximab and lirilumab administration should be delayed and increased monitoring of patients should ensue if any of the following drug-related adverse event(s) occurs:

- Any Grade ≥ 2 ALT, AST, or total bilirubin
- Any Grade ≥ 2 non laboratory non-skin drug related adverse event except for fatigue
- Any Grade ≥ 2 endocrine drug-related adverse event
- Any Grade ≥ 3 skin drug related adverse event
- Any Grade ≥ 3 drug-related laboratory abnormality (except lymphopenia or any electrolyte abnormality without any clinical sequelae that is either spontaneously reversible or resolves with clinical management to grade 2 or less within 72 hours)
- Any AE, laboratory abnormality or inter-current illness, which in the judgment of the investigator, warrants delaying the dose of study medication

Discontinuation of lirilumab will occur in the following situations:

- AST, ALT, or T Bili \geq Grade 3
- Grade 2 AST or ALT and symptomatic liver inflammation (e.g., right upper quadrant tenderness, jaundice)
- AST or ALT $> 3 \times$ ULN and concurrent total bilirubin $> 2 \times$ ULN in the absence of evidence of cholestasis (Hy's law)

7.0 CONCOMITANT THERAPY

7.1 Allowed concomitant therapy

All concomitant medications will be documented in the medical record. Patients should receive full supportive care during study participation, including hematopoietic growth factors, transfusion of blood products, fluid and electrolyte replacement, and antibiotics when appropriate.

7.2 Excluded concomitant therapy

Use of the following therapies is prohibited during the study:

- Cytotoxic chemotherapy
- Immunotherapy (outside of this study)
- Any therapies intended for the treatment of lymphoma/leukemia whether FDA-approved or experimental (outside of this study)
- Steroid therapy for anti-neoplastic intent. Inhaled steroids for asthma, topical steroids, steroids as part of premedication, or replacement/stress corticosteroids are permitted.

8.0 PRETREATMENT EVALUATIONS

1. Pretreatment evaluation will include a complete history and physical examination including vital signs ECOG performance status, height and weight and recording of concurrent medications (within 7 days of the first dose)
2. Complete blood count (hemoglobin, white blood cell count, platelet count, white blood count differential) (within 7 days of the first dose)
3. Clinical laboratory evaluation will include serum sodium, potassium, calcium, BUN, creatinine, glucose, phosphorous, magnesium, albumin, total protein, alkaline phosphatase, total bilirubin, ALT, AST, uric acid, LDH, β -2 microglobulin, serum immunoglobulins, lipase, amylase (within 7 days of the first dose)
4. B, T, NK cell counts and subset analyses on the peripheral blood (within 7 days of the first dose)
5. PT, aPTT (within 7 days of the first dose)
6. Urinalysis (within 7 days of the first dose)
7. HIV Ab, Hepatitis C ab, HBsAg, anti-HBcAb (within 30 days of the first dose)
8. TSH, Free T4 (within 30 days of the first dose)
9. Women of childbearing potential must have a negative serum or urine β -hCG pregnancy test result within 24 hours prior to the first dose of study drugs.
10. 12-lead EKG (within 30 days of the first dose)
11. Bone marrow aspiration and biopsy (within 60 days of the first dose if no intervening treatment for CLL given)
12. CT scan of the neck (if indicated), chest, abdomen, and pelvis with IV and oral contrast, within 30 days of the first dose. Patients with palpable cervical lymphadenopathy noted at screening physical examinations should have imaging of the neck included in their screening imaging studies and at subsequent time points for response assessment. Note: PET scan may be used instead of the CT scan imaging.

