9.0 EVALUATIONS DURING THE STUDY

Cycle 1 Day 1 (Rituximab and Lirilumab)

1. CBC, platelet count and differential, sodium, potassium, calcium, BUN, creatinine, glucose, phosphorous, magnesium, albumin, total protein, alkaline phosphatase, total bilirubin, ALT, AST, uric acid, LDH
2. Vital signs, history and physical examination (Note: history and physical examination within 3 days prior to the Day 1 is acceptable)

Cycle 1 Day 8 (Rituximab) (+/- 2 day)

1. CBC, platelet count and differential, sodium, potassium, calcium, BUN, creatinine, glucose, phosphorous, magnesium, albumin, total protein, alkaline phosphatase, total bilirubin, ALT, AST, uric acid, LDH
2. Vital signs, history and physical examination

Cycle 1 Day 15 (Rituximab) (+/- 2 day)

1. CBC, platelet count and differential, sodium, potassium, calcium, BUN, creatinine, glucose, phosphorous, magnesium, albumin, total protein, alkaline phosphatase, total bilirubin, ALT, AST, uric acid, LDH
2. Vital signs, history and physical examination

Cycle 1 Day 22 (Rituximab) (+/- 2 day)

1. CBC, platelet count and differential, sodium, potassium, calcium, BUN, creatinine, glucose, phosphorous, magnesium, albumin, total protein, alkaline phosphatase, total bilirubin, ALT, AST, uric acid, LDH
2. Vital signs, history and physical examination

Cycle 2 Day 1 (Rituximab and Lirilumab) (+/- 1 week)

1. CBC, platelet count and differential, sodium, potassium, calcium, BUN, creatinine, glucose, phosphorous, magnesium, albumin, total protein, alkaline phosphatase, total bilirubin, ALT, AST, uric acid, LDH, serum immunoglobulins, TSH, Free T4
2. B, T, NK cell counts and subset analyses on the peripheral blood
3. Serum or urine β -hCG pregnancy test (for women of childbearing potential)
4. Vital signs, history and physical examination

Cycle 2 Day 8 (no mAb) (+/- 2 day)

1. CBC, platelet count and differential, sodium, potassium, calcium, BUN, creatinine, glucose, phosphorous, magnesium, albumin, total protein, alkaline phosphatase, total bilirubin, ALT, AST, uric acid, LDH

Cycle 2 Day 15 (no mAb) (+/- 2 day)

1. CBC, platelet count and differential, sodium, potassium, calcium, BUN, creatinine, glucose, phosphorous, magnesium, albumin, total protein, alkaline phosphatase, total bilirubin, ALT, AST, uric acid, LDH
2. Vital signs, history and physical examination

Cycle 2 Day 22 (no mAb) (+/- 2 day)

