13.0 CORRELATIVE STUDIES

Correlative studies relating to immunologic response will be collected on a separate IRB-approved Protocol (PA13-0291).

Approximately 20cc of peripheral blood will be collected at the following time-points (pretreatment, C1D1, C1D8, C2-24D1) and stored in the Leukemia Research Bank. This testing is optional and failure to collect these studies at any of the specified time-points is not a protocol deviation. Approximately 3cc of bone marrow aspirate will be collected at the following time-points (pretreatment, after C3, after C6, after C9, after C12, after C15, after C18, after C21, after C24) and stored in the Leukemia Research Bank. This testing is optional and failure to collect these studies at any of the specified time-points is not a protocol deviation.

Immune Function Studies ([name] [name], MDACC) – This testing is optional and failure to collect these studies at any of the specified time-points is not a protocol deviation. We use 14 color multiparameter flow cytometry to comprehensively analyze NK cell frequencies, phenotype, function (both KIR-ligand mediated and ADCC), homing to sites of tumor (bone marrow and lymph node where available) using the assays described below and in table below. PBMC will be collected on Day 1 (prior to the study drugs) and Day 2 of each cycle (cycles 1-12). In addition, PBMC will be collected on day 8 of cycle 1. Approximately 3cc of bone marrow aspirate will be collected at the following time-points (pretreatment, after C3, after C6, after C9, after C12). To determine whether treatment with a combination of rituximab and lirilumab will enhance CD16 mediated ADCC, NK cells will be stimulated with antibodies against CD20 (Rituximab) to trigger ADCC responses against CD20+ cell lines (Raji and Daudi), in the presence or absence of lirilumab. Function will be assessed using a combination of degranulation (CD107a), effector cytokine production (IFN- γ and TNF- α) and 51chromium release. Each patient will be used as his / her own control and the effect of rituximab and lirilumab combination therapy on NK cell frequency, phenotype and function will be assessed longitudinally. A total of 25 samples will be analyzed per patient. Samples will be sent to the laboratory of [name], MDACC.

Table 13.1. Flow cytometric parameters that will be used to evaluate the impact of rituximab + lirilumab on NK cell phenotype and function

Cell type	Markers & transcription factors	Effector molecules

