Statistical Language for the correlative studies: Descriptive statistics including plots, mean, median and standard deviations will be used to summarize data. For continuous outcomes, t-test and ANOVA will be used to compare outcome measures across patient characteristics. Dunnett's and Tukey's test that properly adjust for multiplicity in multiple tests will be implemented. Pair-wise comparisons will be performed using pre- and post-therapy samples from each patient. The chi-square (c2) test or Fisher's exact test will be used to test the association between two categorical variables such as disease state and performance status. Both univariate and multivariate logistic regressions will be performed to model prognostic factors.

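### The required baseline B/T/NK counts may be drawn while a patient is still on high-dose steroids or immunosuppressants, and no required pre-dose count on Cycle 1 Day 1 replaces them

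*Combined protocol and SAP*

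**What the plan says.** **Baseline draw.** Section 8.0 item 4 lists "B, T, NK cell counts and subset analyses on the peripheral blood (within 7 days of the first dose"). Nothing there ties the draw to the date on which other drugs were stopped.

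**Eligibility.** Exclusion 12 in Section 3.2 concerns patients on more than 10 mg/day of prednisone or equivalent, or on immunosuppressants. Its note adds that they "are eligible provided these drugs are discontinued at least 3 days prior to starting on the study drugs".

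**Next counts.** In Section 9.0 the C1D1 laboratory list starts "CBC, platelet count and differential, sodium, potassium, calcium, BUN, creatinine, glucose, phosphorous, magnesium" and goes on with other chemistry. It contains no B/T/NK counts. They next appear under "Cycle 2 Day 1 (Rituximab and Lirilumab) (+/- 1 week").

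**Research samples.** Section 13.0 plans that "PBMC will be collected on Day 1 (prior to the study drugs) and Day 2 of each cycle (cycles 1-12"), for flow cytometry of NK frequency, phenotype and function, with each patient as their own control. It also banks blood at pretreatment and at C1D1. Both collections are optional, and a missed sample is not a deviation.

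**Analysis.** For the correlative studies Section 14.0 says: "Pair-wise comparisons will be performed using pre- and post-therapy samples from each patient". The Analysis Plan adds mixed-effects models for biomarkers over time. Neither statement says which sample is the baseline or how recent steroid or immunosuppressant use is handled.

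**The concern.** The exploratory objective in Section 1.0 asks about immunological change in response to the study drugs. With no control arm, the pre-treatment sample is the only reference. If it is drawn under drugs that suppress immune cells and those drugs then stop, the first recorded change mixes two causes: withdrawal of the old drugs and exposure to the new ones.

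By the next required count, at Cycle 2 Day 1, the patient is scheduled to have had four rituximab doses and one lirilumab dose. The required series alone cannot then separate the two causes in that patient. A paired test or mixed model would attribute the sum to study treatment.

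At stake is the interpretation of an exploratory biomarker result. Response rate, progression-free survival, overall survival and the stopping rules do not use these counts.

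**Working it through.** **1. Do the windows overlap?** Take the first dose as Day 0.
- Draw permitted (Section 8.0 item 4): Day -7 to Day 0, which is 8 calendar days.
- Restricted drugs may continue (exclusion 12) until 3 days before dosing, that is, until Day -3.
- Days on which a draw can be on-drug: -7, -6, -5, -4, so 4 of the 8. If a last dose on Day -3 itself is counted, 5 of the 8.

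**2. Does a C1D1 pre-dose sample exist elsewhere?** Section 13.0 states 25 immune-function samples per patient. Day 1 and Day 2 of cycles 1 to 12, plus Day 8 of cycle 1, give 2 × 12 + 1 = 25, which reproduces the stated figure. Without the C1D1 pre-dose sample the total would be 24. So an NK-focused C1D1 sample is planned. It is optional, and B and T counts are not listed for it.

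**3. How large could the effect be?** The documents give no figure for this, so what follows is illustration. Assumptions:
- A fraction *f* of patients has an on-drug baseline. These patients shift by *s*, in SDs of the within-patient change among unaffected patients. There is no treatment effect.
- The test is a two-sided 5% paired t-test. *n* = 24 is one full cohort and *n* = 48 both cohorts (Section 14.0).

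Formulas:
- False mean change: *m* = *f* × *s*.
- SD of the change, widened because only a subset shifts: √(1 + *f*(1 − *f*)*s*²).
- Noncentrality: √*n* × *m* / SD.

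For *f* = 0.25, *s* = 1: *m* = 0.25 and SD = √1.1875 = 1.090. Noncentrality is 4.899 × 0.25 / 1.090 = 1.12 at *n* = 24, and 6.928 × 0.25 / 1.090 = 1.59 at *n* = 48.

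For *f* = 0.10, *s* = 1: *m* = 0.10 and SD = √1.09 = 1.044. Noncentrality is 0.47 and 0.66.

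Rejection rates from the noncentral t, with simulation of the mixture agreeing to the rounding shown:

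| Affected | Rebound | n = 24 | n = 48 |
|---|---|---|---|
| 25% | 1 SD | 19% | 34% |
| 25% | 0.5 SD | 9% | 13% |
| 10% | 1 SD | 7% | 10% |
| 10% | 0.5 SD | 6% | 6% |

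The nominal rate is 5%. Shifting every patient by 0.25 SD with the spread unchanged would give 22% at *n* = 24. That overstates the case, because a shift in a subset also widens the SD.

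**4. What does a C1D1 draw change?** On-drug days fall from 4 (or 5) to 0. The sample may still be only 3 days off drug, so recovery may not be complete.

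**The case against.** **The stronger reading.** A reader might infer that withdrawal effects will be counted as a response to lirilumab plus rituximab. The documents do not support that. No section names the screening sample as baseline, and the paired-comparison sentence belongs to the correlative studies, for which Section 13.0 plans a pre-dose C1D1 sample. For NK frequency, phenotype and function, the core of the hypothesis, a suitable reference exists whenever the optional sample is taken. This stands. What remains is the required B/T/NK series, and patients whose optional sample is missing.

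**Few patients may qualify.** Other exclusions in Section 3.2 remove several likely reasons for such drugs: uncontrolled autoimmune cytopenia requiring steroids, autoimmune disease, active graft-versus-host disease or its recent immunosuppression, and organ allografts. To be affected, a patient must also stop in the last days before treatment and be drawn before stopping. This stands too. At 10% affected, the distortion of a single-cohort test is slight.

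**Direction.** One might assume that any rebound raises T and NK counts and so favours the hypothesis. The protocol does not say so. Its hypothesis is better NK-mediated killing, and Section 2.4 reports NK numbers already raised in CLL with defective function.

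**Affected patients can be found.** Concurrent medications are recorded at screening (Section 8.0 item 1) and documented throughout (Section 7.1). That makes a sensitivity analysis possible, but the plan does not call for one.

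**A C1D1 draw is not a full cure.** Correct, as step 4 of the working shows, and the reason why the sensitivity analysis is needed as well.

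**Conclusion.** The point holds as a low-severity design weakness. It rests on three facts in the text: the draw window reaches back further than the stop date in exclusion 12, the required C1D1 list has no B/T/NK counts, and the C1D1 research sample is optional and NK-focused. Changes in the required series may therefore be partly confounded with drug withdrawal in some patients.

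The size is unknown. The figures above rest on assumed fractions and rebounds, and run from near nominal (6%) to 34%. The linked schedule-of-evaluations PDF is not part of the text available and could not be checked.

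**What to change.** 1. Add the B/T/NK counts and subset analyses, pre-dose, to the Cycle 1 Day 1 list in Section 9.0, or move them there from Section 8.0 item 4.
2. State in Section 14.0 that this sample is the baseline for change-from-baseline and mixed-model analyses of these counts.
3. Add a sensitivity analysis that excludes or flags patients with high-dose steroids or immunosuppressants recorded in the 7 days before first dose.

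**Cost.** Blood is already drawn on C1D1. If the screening sample is kept, the cost is one extra flow assay per patient; if it is moved, there is no extra assay. Residual recovery is reduced, not eliminated. No eligibility or washout rule changes.
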